13.11 SUBJECT CONFIDENTIALITY

To maintain subject confidentiality, all laboratory specimens, CRFs, reports, and other records will be identified by a coded number only. Research and clinical records will be stored under controlled access and only the investigative staff will have access to the records. Subject information will not be released without the written permission of the subject, except as necessary for monitoring by the FDA or NIDA. Upon approval of the study by an IRB, an application will be filed with NIDA for a certificate of confidentiality.

13.12 SUBJECT WITHDRAWAL

An investigator may terminate a subject if s/he deems it clinically appropriate or for any of the following reasons: 1) significant side effects from investigational agents, 2) serious or unexpected AEs, 3) inability to comply with the study protocol, 4) protocol violation, or 5) serious intercurrent illness. A subject may withdraw from the study anytime s/he wishes. In the event a subject is discontinued from receiving the investigational agent, s/he will be allowed to continue the psychosocial-behavioral treatment with the approval of the investigator.

Any subject who discontinues prematurely, regardless of the reason, will be requested to return for a final visit to perform the necessary procedures and obtain data for end of study/early termination (see section 14.3).

Study participants withdrawn from the protocol secondary to a medical or psychiatric concern will be referred for appropriate treatment. Subjects will be asked to sign a general consent for the release of information to the referred health care. Study staff may request transportation for emergency treatment of a subject if medically appropriate (e.g., for acutely psychotic or suicidal subjects).

All study participants will be encouraged to carry a wallet card that identifies them as a participant in a clinical research study. The card will provide the name and phone number of the site investigator who can be contacted in the event of an emergency. The card will also instruct the non-study physician rendering emergency care to provide information to the site investigator with regards to that care.

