13.5 PREVENTION OF STUDY DROP-OUTS

Subjects will be encouraged to come for treatment and for the evaluation sessions as described in this protocol. To minimize missed sessions, they will be compensated for their transportation and time spent in completing study assessments. It will be emphasized to subjects during screening that even if they have a relapse they should come to all scheduled appointments. They will be discouraged from using cocaine, but there will be no penalty for relapsing, or for missed sessions.

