13.6 PREMATURE STUDY TERMINATION

Since an intent-to-treat paradigm is being used for this study, subjects will be encouraged to continue completing study visits, study assessments and psychosocial treatment sessions, even if they are unable to tolerate investigational agents. If a subject decides to drop out of the study prior to week 8, s/he will be asked to complete all final assessments (termination) at the time of drop out (see section 14.3). If a subject wishes to stop taking drug but to continue to participate in psychosocial treatment, s/he will continue to have all scheduled assessments according to the protocol and will complete the study at week 8. During the period of psychosocial measures safety and efficacy data will be collected with the exception of data strictly related to patch use. Section 14.5 details the procedures to be followed in the event that a subject dies while participating in the study.

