16.6 SAMPLE SIZE ESTIMATE

The proposed primary outcome measure is the weekly proportion of cocaine non-use days. Power analyses were made based on assumptions of normal distribution, equal correlation between observations at any two times (exchangeable) working correlation and a common standard deviation of 33.5%. These assumptions are based on preliminary results of an eightweek selegiline study (Protocol Number: CS-1017), in which an oral dose of selegiline was compared to placebo in cocaine dependent subjects. We further make the assumption that a 10% increase in the proportion of cocaine non-use days of the STS treatment group over the placebo group would be considered clinically significant. Based on the sample size calculation for GEE procedures proposed by Liu and Liang²⁰, then 110 subjects will be required in each arm to detect this clinically meaningful difference with a power of 80% at the 0.05 level of significance. The retention rates in studies of cocaine addicts currently being conducted by NIDA are approximately 70%, therefore at least 150 subjects should be randomized into each treatment to ensure an adequate sample size at the end of the trial.

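### Section 13.12 lets sites end outcome collection for non-compliance or a protocol violation, against the intent-to-treat follow-up set out in 13.6

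*Protocol*

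**What the plan says.** Protocol 13.12 opens with a discretionary power: "An investigator may terminate a subject if s/he deems it clinically appropriate or for any of the following reasons". Two of the five reasons concern conduct in the study rather than safety: "3) inability to comply with the study protocol, 4) protocol violation, or 5) serious intercurrent illness". Anyone who discontinues early, whatever the cause, "will be requested to return for a final visit to perform the necessary procedures and obtain data for end of study/early termination". A subject taken off the investigational agent is covered by one sentence: "s/he will be allowed to continue the psychosocial-behavioral treatment with the approval of the investigator". Section 13.12 does not mention continued scheduled assessments.

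Protocol 13.6 takes a different line and gives its reason: "Since an intent-to-treat paradigm is being used for this study, subjects will be encouraged to continue completing study visits, study assessments", and it says this applies even to those who cannot tolerate the agent. For a subject who wishes to stop drug but remain in psychosocial treatment, it says that "s/he will continue to have all scheduled assessments according to the protocol and will complete the study at week 8".

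Protocol 13.5 adds that "there will be no penalty for relapsing, or for missed sessions". Section 13.10 pays for visits whether or not medication continues. Section 16.3 defines the intent-to-treat population as everyone randomized. Section 16.4 divides each week's non-use days by that week's non-missing days and compares the arms by generalized estimating equations (GEE).

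**The concern.** Section 13.6 commits the trial to collecting outcomes off treatment because the analysis is by intent-to-treat. Section 13.12 gives each of about 16 sites (Section 7) a power that can end that collection for conduct reasons, and it offers no continued schedule to those it terminates.

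In a cocaine trial, failure to comply plausibly goes with heavier use. The protocol does not say so; it is an inference. If it is right, the weeks lost are not a random sample of weeks. They drop out of the weekly proportions, and ordinary GEE on observed data is generally valid only when missingness is unrelated to outcome given the covariates in the model. An analysis plan can set out how missing weeks are handled, but it cannot recover urine specimens and self-reports that were never taken.

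**Working it through.** **1. The sections side by side**

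| Question | 13.6 (and 13.5) | 13.12 |
|---|---|---|
| Who acts? | Subject cannot tolerate the agent, or wishes to stop it | Investigator, at discretion |
| What follows? | Visits encouraged; full schedule to week 8 for those staying in psychosocial treatment | One final visit requested |
| Is approval needed? | None mentioned | Yes, for psychosocial treatment off the agent |
| Missed sessions | No penalty (13.5) | Failure to comply is a ground for termination |

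The sections interlock. In 13.6 the week-8 schedule goes to those who stay in psychosocial treatment; in 13.12 staying in that treatment after being taken off the agent needs approval. The approval clause therefore reaches the assessments, but only through 13.6. *Terminate* is not defined. The section title, the early-termination visit and the separate sentence about the agent favour the reading that the subject leaves the study.

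**2. The plan's own figures (16.6)**

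Inputs: SD 33.5 points, difference 10 points (read as absolute), two-sided 0.05, power 80%, eight weekly values, exchangeable correlation ρ (value not stated).

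- n per arm = 176.2 × (1 + 7ρ)/8, which returns the stated 110 at ρ of about 0.57.
- The plan says "therefore at least 150 subjects should be randomized into each treatment". The ratio 110/150 = 0.733 is slightly above the stated retention of about 70%, which leaves 150 × 0.70 = 105.

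The gap between 105 and 110 is a separate sample-size matter and adds no weight here. What matters is that the roughly 30% loss is not split by cause, so the share due to investigator termination is unknown.

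**3. Bias illustration (all inputs assumed)**

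Let a share f of an arm be terminated, with a true non-use proportion D points below that of the retained subjects. If all their weeks are missing, that arm's observed mean is too high by f × D. The treatment difference shifts by (f on STS − f on placebo) × D.

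| f on STS | f on placebo | D = 10 | D = 20 | D = 30 |
|---|---|---|---|---|
| 5% | 5% | 0 | 0 | 0 |
| 5% | 10% | −0.5 | −1.0 | −1.5 |

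Negative values shrink an STS advantage; exchanging the two rates reverses the sign. The second row averages 7.5% per arm, equal to a quarter of the expected loss (0.30 × 0.25 = 0.075). Weeks before termination do enter the GEE. If termination came on average at mid-treatment, the shift would roughly halve, to 0.25 to 0.75 points.

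**The case against.** The best defence is that the two sections can be read together. The week-8 sentence in 13.6 covers a subject who chooses to stop drug, while 13.12 is a permissive power for the investigator and revokes nothing. Section 13.5 protects subjects who relapse or miss sessions, and cocaine use is nowhere listed as a violation, so 13.12 need not remove the heaviest users. This shows that the harm is not inevitable. It does not remove the clash: the intent-to-treat rationale covers every randomized subject whoever decides to stop, and 13.12 sets no limit on what counts as failure to comply.

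Four stronger readings are tempting, and the documents do not support them.

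- A reader might infer that the protocol treats stopping patches and leaving the study as one event. It does not: 13.6, 13.10 and 13.12 each use separate wording for the agent. What is missing is a statement that ending treatment does not end data collection.
- A reader might infer an explicit approval condition on assessments. The approval in 13.12 attaches to psychosocial treatment only.
- A reader might infer a definite gain in retention. If 10%, 25% or 50% of the losses were terminations whose assessments continued, 150 × (0.70 + 0.30 × share) gives 109.5, 116.3 or 127.5 per arm. Those shares have no source, and the sum supposes that every such subject stays to week 8, which is least likely in those removed for not complying.
- A reader might take 1 to 1.5 points as the bias. That needs all eight weeks missing and a 5-point difference in termination between double-blind arms. At a 10% share, terminations average 3% per arm, so the difference would require 5.5% against 0.5%.

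**Conclusion.** The point holds as an inconsistency in follow-up rules that can produce avoidable, plausibly outcome-related missing data. It rests on two readings: that *terminate* in 13.12 means leaving the study, and that non-compliance tracks cocaine use. Neither is stated, though the text favours the first and the second is reasonable in this population.

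No bias is demonstrated. Its size and direction cannot be obtained from the protocol; it is zero with equal rates and equal deficits, and under the assumptions shown it is small beside the 10-point target. The case for change is that the correction is cheap and must be made before data are lost.

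**What to change.** Reconcile 13.5, 13.6 and 13.12 with two statements on data collection:

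1. Stopping patches, non-compliance or a protocol violation does not by itself end scheduled self-report and urine benzoylecgonine collection to week 8.
2. Investigator approval of continued psychosocial treatment does not gate those assessments.

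Leave as they are the clinical grounds for stopping patches and the investigator's power to end participation on medical or psychiatric grounds. A rule that only withdrawn consent or lost contact ends data collection would go too far, because it would remove that power.

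The cost is a few sentences and some further visits at the existing $10 each, which 13.10 already makes payable off medication. For example, a subject who would otherwise leave after week 4 has 4 × 3 = 12 treatment visits left, or $120, within the existing $370 maximum. Site time and central assays for those visits add to this; the protocol does not price them.

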The investigational drug to be investigated in this study is Selegiline. Selegiline is an irreversible selective inhibitor of monoamine oxidase type B (MAO-B). It is hypothesized that selegiline may affect cocaine addiction through several potential mechanisms of action. Inhibition of MAO-B increases concentrations of dopamine and other neurotransmitters, which may help restore normal levels in subjects whose use of cocaine has disrupted levels of these neurotransmitters. Another hypothesis is that selegiline metabolites may provide a low, but sustained therapeutically effective level of substitution for the stimulating effects of cocaine. There is no evidence that selegiline causes euphoria or dependence. The high degree of MAO-B inhibition achieved is associated with functional increases in dopamine concentrations. Dopamine is thought to be central to the reinforcing effects of cocaine. While dopamine depletion has been associated with chronic cocaine use and withdrawal symptomatology, it is widely accepted that euphoria associated with cocaine use is a result of action at reward pathways via antagonist properties at the dopamine transporter site. Cocaine also inhibits reuptake of the neurotransmitters serotonin and norepinephrine. These actions are thought to underlie cocaine's potent reinforcing properties. With prolonged use, cocaine may deplete these neurotransmitters, affect postsynaptic receptor density, and elicit an overall dysregulation of these neurotransmitter systems. These long-term consequences may account for the post-cocaine dysphoria thought to contribute to relapse.^{1, 2,3}

Pharmacology laboratory studies in humans and animals suggests that selegiline blunts the reinforcing effect of cocaine, while a pilot outpatient clinical trial, with a sustained release oral selegiline, reduced cocaine use.⁴

Selegiline was first tested for cocaine dependence using a sustained-release oral dosage formulation. Initial, protocol-specified analyses of a phase 2, double-blind, placebo-controlled clinical trial showed a trend toward decreased cocaine use. However, subsequent analysis according to FDA's recommendations showed a statistically significant effect of selegiline over placebo. Currently, this is the strongest positive treatment signal seen in clinical trials for cocaine dependence.⁴ However, sustained-release selegiline is no longer available.

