11.4 APPLICATION OF STS/PLACEBO PATCHES

The patch is to be applied to a clean, hairless area on the subject's upper torso or upper thigh (see Appendix II). The skin at application site should not be oily, irritated, broken, scarred or calloused. The patch application site should be rotated daily to allow for multiple applications. Prior to application, the site should be gently washed, not rubbed, with lukewarm soapsuds avoiding any local irritation. The site should be rinsed with clear water and gently towel dried. The patch is removed after 24 hours and replaced with a new patch within an hour of removal. Showering or bathing should be scheduled just prior to reapplication of the patch.

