13.8 MAO-I SAFETY

No significant changes in blood pressure have been observed in the Somerset sponsored clinical trials in depression or in the NIDA clinical pharmacology studies with cocaine and STS. Based on studies performed by Somerset, tyramine dietary restrictions have been removed from STS protocols. In the unlikely event of a hypertensive crisis and/or STS overdose, the transdermal system should be discontinued and the underlying skin washed with soap and cold water to remove any residual investigational agent.

Vital signs will be measured to detect a pressor response in subjects receiving MAO inhibitors. Full reliance should not be placed on blood pressure readings, and the subject should also be observed for clinical signs of a sympathomimetic reaction. Accordingly, clinical judgment should be exercised regarding discontinuation of investigational agent if symptoms such as palpitations, tachycardia, sense of constriction in the throat or chest, or frequent headaches occur during the trial.

Subjects will be instructed to report promptly the occurrence of headache or other unusual symptoms, i.e., palpitations and/or tachycardia, a sense of constriction in the throat or chest, sweating, dizziness, neck stiffness, nausea, or vomiting.

Subjects will be cautioned not to take concomitant medications, whether prescription or OTC medications, without consulting the site investigator or physician designee.

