13.9 MAINTAINING AND BREAKING STUDY BLIND

The decision to break the study blind for an individual subject lies with the site investigator and study principal investigator or with the NIDA medical monitor, but should be resorted to only in cases of life-threatening emergency when knowledge of the treatment arm investigational agent will influence clinical management.

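### The emergency wallet card as specified in section 13.12 does not tell an outside physician that the holder may be wearing an MAO-inhibitor patch

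*Protocol*

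**What the plan says.** Section 13.12 describes the card in three sentences. Subjects are "encouraged to carry a wallet card that identifies them as a participant in a clinical research study". On the contact it says: "The card will provide the name and phone number of the site investigator who can be contacted in the event of an emergency". Finally, the card will "instruct the non-study physician rendering emergency care to provide information to the site investigator with regards to that care". Nothing else in the protocol text at hand adds to the card's content.

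Other sections bear on what an emergency physician would need to know:

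- Section 4 gives the drug class: "Selegiline is an irreversible selective inhibitor of monoamine oxidase type B".
- Section 11.4 puts the patch on the "upper torso or upper thigh".
- Section 13.8 says that in a hypertensive crisis or an overdose "the transdermal system should be discontinued and the underlying skin washed with soap and cold water". It also places a duty on the subject: "Subjects will be cautioned not to take concomitant medications" without consulting the site.
- Section 13.9 leaves unblinding to the investigators or the NIDA medical monitor and says it "should be resorted to only in cases of life-threatening emergency when knowledge of the treatment arm investigational agent will influence clinical management".
- Section 13.13 lists drugs not to be used with the study patch. They include meperidine and other opiates, epinephrine, norepinephrine, dopamine, metoclopramide and antipsychotics.

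**The concern.** The card's intended reader is a physician outside the study who is treating a subject in an emergency. The most useful fact for that reader is that the patient may have an irreversible MAO inhibitor on board, delivered by a patch that may still be on the skin. The specified content leaves this out. The only instruction on the card sends information from the physician to the study, not the other way.

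What is at stake is the safety of individual subjects: a drug that the protocol itself rules out with the patch could be given unknowingly, or the removal and washing step in section 13.8 could be missed. No efficacy result, error rate or power figure depends on this.

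**Working it through.** The plan states no figure on this point and there is nothing to recompute. The check sets the card specification beside what the protocol says elsewhere.

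**Step 1: the card content, item by item (section 13.12).**

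| Card item | Names the drug? | Names the class? | Mentions a patch? |
|---|---|---|---|
| Holder takes part in a research study | No | No | No |
| Site investigator's name and phone number | No | No | No |
| Outside physician to report the care to the investigator | No | No | No |

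So 0 of 3 specified items carry the information.

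**Step 2: does the protocol treat the missing fact as important?** It does.

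- Section 4 describes the MAO-B inhibition as irreversible, so removing the patch does not by itself end the interaction risk.
- Section 13.13 rules out several drugs that emergency care could plausibly use.
- The hypertensive-crisis step in section 13.8 requires someone to know that there is a patch. At the sites named in section 11.4 it would usually lie under clothing, so the physician must know to look.

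**Step 3: do the other safeguards cover the gap?** Each depends on a condition that may fail in an emergency.

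| Safeguard | What it depends on |
|---|---|
| Contact number (13.12) | The card is carried, the investigator is reached, and the call precedes the drug |
| Caution about other medications (13.8) | A subject who can communicate |
| Unblinding (13.9) | Reaching study personnel, and having a reason to ask |

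Section 13.12 itself foresees emergency transport of acutely psychotic or suicidal subjects, who may not be able to give a reliable drug history. A physician with no hint that an MAO inhibitor is possible also has little reason to seek unblinding.

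**Step 4: is there a conflict with section 13.13?** No. That section governs what investigators approve and what subjects take; it places no duty on an outside physician. The card is therefore an incomplete safeguard and does not contradict 13.13.

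**Step 5: would naming the drug break the blind?** No. Stating that the holder receives selegiline or placebo reveals only the two possible assignments, which apply to every subject.

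**Step 6: size.** The synopsis plans 300 subjects, 150 per group, so the share assigned to active patches is 150 / 300 = 50%, for 8 weeks of treatment. The number who would benefit from a better card also depends on how often subjects receive outside emergency care, how many carry the card, and how often a call fails. The protocol gives none of these, so no estimate is offered.

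**The case against.** The strongest reply is that this argues from silence. Section 13.12 does not call its list complete, and the printed card, the appendices and the operations manual are not at hand. Exact card wording is often settled in such material, and nothing in 13.12 prevents the sponsor from naming the drug. That limit stands: the finding applies to the specification and cannot say what was printed.

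Second, the phone number exists so that an outside physician can reach the study in an emergency, and the request to report the care should itself prompt contact. This is fair, and the number deserves credit. But reporting care can happen after the care has been given, and a card made exactly as written gives no reason to call beforehand.

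Third, harm needs several things to coincide: outside emergency care, a subject who cannot speak, no timely call, and either an interacting drug or an overlooked patch in a crisis that section 13.8 regards as unlikely. The tyramine data for the 20 mg patch in section 4 and the preliminary cocaine-interaction data in section 4.5 are reassuring. This limits the expected benefit, which cannot be quantified. Those studies did not, however, test the drugs listed in section 13.13, and the improvement is cheap enough not to need a large expected benefit.

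Fourth, carrying the card is only encouraged, so better wording cannot help a subject who leaves it at home. That also stands.

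**Conclusion.** The point holds as a modest safety improvement that should be made. The card content that section 13.12 specifies omits the drug, its class and the patch (0 of 3 items), and the remaining safeguards rely on a subject who can speak or a call that is made and answered in time. It concerns the half of the subjects assigned to active patches, 150 of 300, during 8 weeks of treatment; how many would benefit cannot be estimated from the protocol. Efficacy analysis, alpha and power are untouched.

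The conclusion assumes that the card would be produced as section 13.12 describes it. If the printed card already carries a drug warning, the only action is to bring 13.12 into line with it. Confidence is medium for that reason.

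**What to change.** Add to the card specification in section 13.12 a statement along these lines:

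*May be receiving selegiline (an MAO inhibitor) or placebo by skin patch. Check for MAO-inhibitor interactions and, where time allows, call the site investigator before giving medication. Do not delay life-saving treatment.*

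Do not print the section 13.13 list on the card: without qualification it could hold back emergency drugs that the patient needs. Sections 13.9 and 13.13 can stay as they are, and the words *or placebo* preserve the blind.

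The cost is a few lines of card text, a clinical safety check of the wording, and IRB approval. There are two downsides: the card would reveal the type of drug to anyone who reads it, and because carrying it remains voluntary, the gap is narrowed and not closed.
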